That human migraine can be treated effectively with episodic injections of anti-CGRP antibodies begets the question whether these newly prescribe-able medications can be repurposed for other trigeminal pain conditions and the related glossopharyngeal cranial nerve pain which are known to involve neurogenic inflammation. Another pain condition with poor treatment options for sufferers is fibromyalgia, especially fibromyalgia with associated small fiber neuropathy which leads to systemic de-afferentiation of patients' sensory system. In this condition, there is strong evidence for presence of neurogenic inflammation, and it is a rational concept that neurogenic inflammation contributes to disease pathogenesis and especially to the dominating clinical symptom of pain.

We propose to treat patients (targeting enrollment of n=20) who suffer from trigeminal or glossopharyngeal nerve pain in the context of painful small fiber neuropathy. We predict that recruitment of these patients will not be a challenge in the PI's clinics, based on previous experience and ongoing referral practice. Primary criterion is to establish an excellent safety profile that recapitulates the favorable data recorded in migraineurs. The primary pain-related objective is reduction of pain and reduced use of rescue and other anti-pain medications.

Secondary pain-related objectives are improvement of circadian rhythm impairment by galcanezumab, improvement of serum markers for chronic inflammation including protein/peptide as well as small non-coding RNA molecules, and discovery of DNA polymorphisms that predispose treated patients to accentuated responses of either lack of response or particularly potent response.

Clinical Collaborators

[name] MD, Duke Neurology
[name] MD

Hypothesis/ Purpose

We hypothesize that the proposed galcanezumab regimen will be found safe in our patient population, and that provisional evidence of its effectiveness will become apparent. We envision galcanezumab to target neurogenic inflammation in the trigeminal territory and neurogenic inflammation associated with small fiber neuropathy/fibromyalgia.

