Treatment with a CGRP-neutralizing antibody, galcanezumab in this specific patient group, being seen in the PI's clinics on a regular basis, is rooted in the rationale of unmistakable presence of clinical signs of neurogenic inflammation in the painful territory, such as episodic swelling combined with redness/hyperemia, also relief by external cold application which typically patients with trigeminal or glossopharyngeal nerve pain abhor.

Primary Outcome Measures

Primary criterion is to establish an excellent safety profile that recapitulates the favorable data recorded in migraineurs. The primary pain-related objective is reduction of pain and reduced use of rescue and other anti-pain medication.

Inclusion Criteria

- G50.1 diagnosis (can encompass an add-on G50.0 and other headache G43.... codes), or G52.1 diagnosis code (with explicit mentioning of pain of glossopharyngeal origin) **AND** small fiber neuropathy diagnostic codes G63.3, G60.8, G62.8 (can encompass fibromyalgia diagnostic code M79.7)
- 18-80 years old
- not allergic to galcanezumab and other hu mAb biologics

Exclusion Criteria

- allergic to galcanezumab and other hu mAb biologics
- pregnancy

Study Design / Overview

We propose to treat patients open label for 12 weeks, with galcanezumab, supplied by Eli Lilly, as add-on to all other therapeutic measures. We propose to use a 240mg/120mg/120mg regime, with subcutaneous (self-)injections every 4 weeks.

To reflect pain experienced by patients, the primary read-out is pain level on a 0-10 visual analog scale. We will be prompting patients to record a daily summary read at the end of each day.

[figure not shown]
The second criterion is reduction of intake of anti-pain medication (rescue PRN or regular) which the patients will record.

Chronic pain, especially fibromyalgia pain combined with trigeminal or glossopharyngeal nerve pain, is a potent disruptor of circadian rhythm. We strongly believe that this is an important and hitherto under-appreciated contributor to individual disease burden. Therefore, the third criterion is assessment of circadian rhythm function. We will assess this by having the patient rate subjectively how energetic they feel during awake day-time. Wearable activity monitors will be used to address how many hours patients sleep per

24h period, with detailed focus on total duration of sleep/rest and duration of night-time sleep only.

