Before treatment, there will be a 4 week observation-only period, and another one 8 weeks post-treatment, so that the total study period will be 6 months.

We aim for 20 patients to be included in this study.

see more detailed graphics in the next section

In terms of ancillary, laboratory-based studies, we intend to draw blood before treatment and at the 45-, 75-, 105- and 135-day of treatment time-points. We will measure cytokine/chemokine/lipid pain- and inflammation markers in patients' serum, also determine microRNA in their serum, and genomic DNA polymorphisms, the latter only at baseline. Please see next section for more detail.

To establish safety of the anti-CGRP treatment in this patient cohort, blood draw at baseline and at the 45-, 75-, 105- and 135-days of treatment time-points will also include routine systemic sentinel/surveillance markers, namely comprehensive metabolic panel and complete blood count with differential, and complete urinalysis. No more than 45 ml of blood will be collected at any given visit.

In terms of additional safety parameters, we propose an open, patient-kept side-effect log, plus home-based recordings of blood pressure, heart rate and weight at a frequency of 2x/week.

We will set up a data and safety monitoring board for proper management and oversight of data handling and patient safety-related issue; see next section.

[figure not shown]
We expect to observe effective treatment, at least in a significant subgroup of patients. Effectiveness of treatment, also magnitude of any observed therapeutic effect will be correlated with the pain/inflammation proteinaceous, lipid and RNA-based biomarkers in patients' serum, also with any polymorphisms in the patients' genomic DNA.

We also expect galcanezumab treatment to show another record of safe treatment, our expectation sculpted by analysis of in-depth data from treatment of migraineurs. Yet we will remain vigilant and implement the proposed safety sentinel measures in order not to miss adverse effects. This appears prudent because trigeminal or glossopharyngeal nerve pain plus small-fiber neuropathy is a different underlying disorder than migraine, likely representing a higher prevalence in peri-menopausal female patients. We also believe it is likely that level of chronic pain suffering-associated stress will be higher in our study population than in migraineurs.

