AE reporting will be conducted as detailed in this section. To remember, this is an Investigator Initiated Trial (IIT) meaning that the PI, his clinical team and their institutional safety board (Duke IRB) are/represent the Investigator and Sponsor, resulting in the above AE, SAE, SUSAR and other reporting requirements and mandatory chains of communication. Updating and reporting of IIT progress to Eli Lilly will be conducted under separate agreement. Effective communication between the PI, his clinical team, the Duke IRB and Eli Lilly will be implemented. This will help minimize risk and enhance safety for study participants, also by leveraging the wealth of information that Eli Lilly has gathered on galcanezumab.

8) Inclusion/exclusion criteria detail

Inclusion criteria, in terms of diagnosis are: the patient has an assigned diagnosis of non-neuropathic trigeminal nerve pain G50.1, with all its permutations listed in the ICD10 explicitly allowed. Co-morbid trigeminal neuralgia G50.0 and G43. ... related headache codes are allowed. As an alternative to trigeminal nerve pain G50.1, glossopharyngeal nerve pain will be another inclusion criterion, with a G52.1 diagnosis and explicit mentioning of pain mediated by or in the innervation territory of the glossopharyngeal nerve. In addition, patients have to be diagnosed with a painful small fiber neuropathy. This diagnosis is based on a skin biopsy or biopsy of an innervated surface epithelium with nerve fiber density count. The required ICD10 diagnostic codes are G63.3, G60.8, G62.8. Co-morbidity with a fibromyalgia-related disorder will be allowed, typically summarized under a diagnosis code of M79.7.

Importantly, the PI's clinics and referring clinics to his clinics encounter patients with this diagnosis on a high frequency.

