For the rationale to have the above specific inclusion criteria, see "Abstract" on p3, and "Purpose" on p4. Very briefly, (i) access to the respective patient population appears not limited, (ii) neurogenic inflammation is strongly considered to function pro-algesically in trigeminal nerve pain (and by inference in glossopharyngeal nerve pain) **and** in small fiber neuropathy-associated pain, (iii) trigeminal or glossopharyngeal nerve pain associated with small fiber neuropathy/ fibromyalgia appears to be a hitherto unrecognized particular variant of painful cranial nerve disorder. Re point (i), this could be related to the development that the PI's clinics have become US national go-to centers for painful cranial nerve disorders. Especially re argument (iii), the phase Ib treatment study as proposed here will help us to define better this new pain disorder, which we strongly feel deserves separate and explicit recognition, also in terms of treatment response.

Age-wise, the protocol applies to patients between 18 and 80 years old.

Patients that have a history of allergy or allergy-like incompatibility with a biologic that contains a human or humanized monoclonal antibody will be excluded.

Likewise female patients of child-bearing age who are or want to become pregnant will be excluded. In case such a patient intends to participate, then she has to commit to a pregnancy prevention regimen that is based on hormonal contraceptive or intra-uterine device. This is stated explicitly in the Informed Consent Form.

These exclusion/ inclusion-relevant points will be ascertained and discussed explicitly during the initial visit. Agreement between patient seeking enrollment and investigator will be documented in the patient's electronic health record and in the ICF. As for the pregnancy issue, in female patients of child-bearing age, a pregnancy test will be administered at first visit.

9) Standard-of-care vs activities to be carried by the protocol

All activities related to the study as listed under **1) Timeline** will be carried by the protocol. In case safety-related laboratory parameters (comprehensive metabolic panel, complete blood count and urine-analysis) will be needed under a standard-of-care approach, then this will be followed and resulting data will be perused for this study. In all other cases and circumstances, the clinical activities will be carried by this protocol.

10) Recruitment plan

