Patients will be recruited via the PI's clinics at Duke University, the Duke Clinics that typically refer to her attention and outside clinics and providers that refer to her as well, and DEDUCE database. In case of slow recruitment patient self-help and patient advocacy associations in the facial pain arena will be informed of the ongoing study to assist with recruitment. These organizations (Facial Pain Research Foundations, Facial Pain Association) are well-known to the PI.

11) Brief Statistical Analysis Plan

Only patients who complete the study will be included in the statistical analysis.

Response to treatment will be assessed by comparing pain metrics during the 90-day treatment period vs averaged 30 day "run-in". Outcome variables will consist of selected readout parameters of "pain metrics", namely pain subjective rating on VAS (0-10) and medication co-use. Additional outcome variables include circadian rhythm-associated metrics. A daily readout for each variable will be entered into their log by each patient, or by automatic activity reads from their motion tracking device. In similar manner, we will compare pain metrics during the 90-day treatment period vs 60-day post-treatment observation.

We intend to conduct the study with an n=20 patients to successfully complete the study. This selected number appears the most feasible and practicable number. We are confident that with an n=20 we will be in a position to do justice to the objective of initial assessment of the safety of galcanezumab in the condition under study, trigeminal or glossopharyngeal pain in the context of painful small fiber neuropathy/fibromyalgia.

Following completion of the study, we will have estimates of effect sizes and corresponding 95% confidence intervals providing information on the precision of the statistical estimates of treatment effect. Power analysis will be performed based on these estimates and will provide us with guidance for sample sizes of follow-up studies that aim for demonstrating effectiveness.

The statistical analysis will be based on a linear mixed model for repeated measures. The

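### Eligibility does not address current or recent use of CGRP-pathway drugs, so in some patients the run-in and baseline serum CGRP may already reflect the mechanism under test

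*Combined protocol and SAP*

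**What the plan says.** Study Design / Overview describes open-label galcanezumab given "as add-on to all other therapeutic measures"; no drug class is excepted.

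Eligibility appears twice:
- The overview excludes patients who are "allergic to galcanezumab and other hu mAb biologics" and those who are pregnant.
- Section 8 states: "Patients that have a history of allergy or allergy-like incompatibility with a biologic that contains a human or humanized monoclonal antibody will be excluded". It also excludes women who are, or want to become, pregnant, and attaches a contraception condition.

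On diagnosis, section 8 says: "Co-morbid trigeminal neuralgia G50.0 and G43. ... related headache codes are allowed". The overview inclusion criteria likewise admit G43 codes.

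The Abstract gives the background: "human migraine can be treated effectively with episodic injections of anti-CGRP antibodies begets the question whether these newly prescribe-able medications" can be repurposed. It mentions gepants only as trial evidence for the mechanism.

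On timing: "Before treatment, there will be a 4 week observation-only period, and another one 8 weeks post-treatment". Section 11 compares pain metrics in the 90-day treatment period with the averaged 30-day run-in, and separately with the 60-day post-treatment period. Treatment enters a mixed model as a binary covariate. The analysis is limited to completers, with 20 intended. The resulting effect sizes will guide sample sizes for follow-up studies.

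Section 2 lists CGRP among the serum markers measured before and during treatment, and plans to relate high and low or non-response to the biomarkers.

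**The concern.** The eligibility text screens for allergy to an antibody biologic but not for use of one. A patient with trigeminal pain, small fiber neuropathy and migraine who already takes galcanezumab, or another drug acting on the same pathway, meets every written criterion. No washout, stable-background rule, stratum or covariate covers this case.

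There is no control arm, so each patient's run-in is the only pre-treatment reference. If it already contains CGRP blockade, the change from run-in no longer measures what starting CGRP blockade does. Four uses of the data are exposed:
- the pain effect estimate and its confidence interval;
- the sample sizes of later studies planned from that estimate;
- the responder labels, because a patient may look like a non-responder on account of a background drug rather than biology;
- baseline serum CGRP and the safety summary, which would mix patients under single and double blockade.

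With 20 completers, each such patient is 1/20 = 5% of the pain analysis.

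**Working it through.** **Step 1: is such a patient eligible?** Setting the passages side by side: migraine codes are allowed (overview; section 8), all background treatment may continue (Study Design / Overview), and the exclusions are allergy and pregnancy or the wish for it (overview; section 8). Nothing written keeps the patient out.

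**Step 2: does it reach the analysis?** The contrast is within patient, treatment period against run-in (section 11). The only named treatment term is binary, and no term for background CGRP blockade is named. Such patients are therefore pooled with the rest.

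**Step 3: in which direction?** That depends on what happens to the other drug, which no rule fixes.
- If it continues unchanged and galcanezumab adds little, these patients show little change and the mean moves toward zero. The comparison with the post-treatment period is affected in the same way.
- If it is stopped around the run-in, run-in pain may rise. Restoring the lost blockade would then count as new benefit, and the mean moves upward.
- If it is stopped during treatment and counted as pain medication, it could register as reduced medication use, which is itself an outcome.

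**Step 4: how large could the dilution be?** There is no plan figure to reproduce: section 11 chooses n = 20 for feasibility and gives no power, effect size or SD. Let f be the share of such patients and r the fraction of the effect they still gain. Both are assumptions. With the other drug unchanged and the SD held fixed:

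observed mean effect / effect without such patients: m = 1 − f(1 − r)

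sample multiplier for equal power = 1/m²

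| f | m, r = 0 | multiplier | m, r = 0.5 | multiplier |
|---|---|---|---|---|
| 10% (2 of 20) | 0.90 | 1/0.81 = 1.23 | 0.95 | 1/0.9025 = 1.11 |
| 20% (4 of 20) | 0.80 | 1/0.64 = 1.56 | 0.90 | 1/0.81 = 1.23 |
| 30% (6 of 20) | 0.70 | 1/0.49 = 2.04 | 0.85 | 1/0.7225 = 1.38 |

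**Step 5: the same on the scale of 20 patients.** I use a two-sided paired t-test at 0.05 (sidedness is assumed, and this is simpler than the planned mixed model). A standardized change of 0.66 SD has 80% power with n = 20. Holding that effect and the SD fixed, 2, 4 or 6 such patients lower power to 71%, 61% or 50% if they gain nothing, and to 76%, 71% or 66% if they gain half.

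**Step 6: what does dropping them recover?** The effect returns to full size, but n falls to 20(1 − f), a penalty of 1/(1 − f) = 1.11, 1.25 or 1.43. With 4 such patients and r = 0, power is 61% pooled, 69% after dropping them (n = 16) and 80% had all 20 been free of such drugs. With r = 0.5 the pooled power is 71%, so dropping them gains no power. It then serves interpretation only.

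**The case against.** The strongest reply is that this is an add-on trial. Nobody's run-in is untreated by design, and the declared question is the change over each patient's own background. On that view, a small change in someone already under CGRP blockade is effect heterogeneity, not bias. The protocol expects benefit in a subgroup and plans to study low and non-responders. The trial is also a safety-first pilot with no power target, its daily log records all medications, and section 7 asks the investigator to weigh concomitant treatment when judging causality.

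Much of this stands. It would be wrong to say that these patients alone lack an untreated baseline. The precise statement is that their run-in is not free of the mechanism under test. A reader might also infer that the pain effect is diluted. The documents do not support that as fact: it requires that such patients enrol, that they gain less from galcanezumab, and that their other drug stays constant. If the last fails, the shift can reverse. Nor do the documents say that gepants are in clinical use for migraine. The multipliers do not show this trial to be underpowered, since it sets no power target.

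The gap itself is not answered. Background CGRP blockade differs from other background therapy because it is the same mechanism as the study drug. The log makes these patients identifiable, but no analysis uses it for this purpose. The schedule figure and consent form are not in the text available here, so a restriction there cannot be ruled out; neither written eligibility section contains one.

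**Conclusion.** The point holds as a design gap that should be closed. As written, patients on current or recent CGRP-pathway drugs may enrol and are pooled into the pain contrast, the responder comparisons and the effect size that will guide later studies. No figure in the documents is contradicted.

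The size is unknown, because neither f nor r is given. For f between 10% and 30%, the mean effect would fall to 90–70% of its value if these patients gain nothing, or to 95–85% if they gain half. Both ranges assume an unchanged background drug and a fixed SD. If the other drug is stopped around the run-in, the distortion may instead be upward, and these figures do not apply. If no such patient enrols, there is no effect.

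**What to change.** Add current or recent use of galcanezumab or another CGRP-pathway drug to the exclusion criteria, both in the overview and in section 8. The look-back is for the investigators to set.

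If such patients are to be kept, then in section 11:
- flag them from baseline treatment history and the daily medication log described in section 4;
- prespecify the run-in versus treatment pain contrast, and the responder and biomarker analyses, without them;
- still report their safety data, and say so explicitly, because section 11 now limits the statistical analysis to completers and defines no safety set.

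The exclusion costs one line and a slightly smaller recruitment pool, in a setting where the protocol expects no difficulty recruiting. The flag costs patients in the pain analysis and, as Step 6 shows, recovers at best part of the lost precision, so exclusion at entry is the cleaner choice for the pain question.

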We also expect that the proposed studies will be very important for guiding future, more in-depth studies involving larger patient cohorts, placebo-controlled/double-blinded studies, which will possibly lead us toward a personalized-medicine approach.

Study Design Detail

1) Schedule of Activities over Time

2) Blood draw: detailed analysis

Before treatment, and at 45th, 75th, 105th and 135th day of treatment, we propose to assess the following blood parameters, related to pain-associated biomarkers in the systemic circulation.

For this, we propose to study cytokine/chemokine pain- and inflammation markers in patients' serum, using commercially available protein multiplex detection assays. In serum, the following 39 cytokines/chemokines/lipid mediators/peptides will be measured: EPO, GM-CSF, IFN- γ , IL-1 β , IL-2, IL-4, IL-5, IL-6, IL-9, IL-10, IL-12/IL-23p40, IL-12p70, IL-13, IL-15, IL-16, IL-17A, IL-17A/F, IL-17C, IL-17E/IL-25, IL-17F, IL-21, IL-22, IL-23, IL-27p28/IL-30, IL-31, IL-33, IP-10, KC/GRO, MCP-1, MIP-1 α , MIP-1 β , MIP-2, MIP-3 α , TNF- α , VEGF-A, TGF- β , CGRP, Resolvin-D1, Prostaglandin-E2. For these measurements, we will be using a human 35-plex ELISA (U-PLEX Biomarkers) and single ELISAs (Signosis; Cayman).

These are key mediators and indicators of pain and inflammation. We believe it will be feasible to conduct these assays. For each marker there is sufficient evidence supporting its role in pro-algesic inflammation or organismal response to tissue damage. We are

convinced that their ensemble will prove a powerful source of mechanistic data that will elucidate treatment responses to galcanezumab in our patient population.

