time course of pain metrics reported during the treatment period will be compared with metrics during the run-in baseline. The covariance matrix describing the nature of correlations between repeated measures will be selected based on Akaike information criterion and Bayesian information criterion, as guided by our statistics software, SAS/STAT15.1. p-values <0.05 will be considered statistically significant. Effects of treatments will be investigated with the introduction of treatment as a binary covariate (we will evaluate the effects of pre- and post-treatment in two different models).

Patients' anti-pain treatment response will be correlated with blood markers for pain, inflammation and miRNA, and also for genomic markers. This approach will be pursued in order to identify candidate biomarkers that pre-dispose patients to experience an effective or non-effective treatment response. In case of recording any particular safety-related parameters, correlation of these markers to safety metrics will also be conducted. Association between molecular biomarkers and pain- and activity-related metrics will be evaluated (i) at each time point separately using a linear regression model; (ii) by modeling the association across all time points and including time covariate in the linear regression model. The ensemble of these approaches will help determine the periods when pain or activity-related metrics and molecular markers co-evolve and become highly correlated.

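### TGF-β, VEGF-A and prostaglandin E2 are measured in serum but read as circulating biomarkers; the regressions ignore the part added in the tube, whose size the documents do not give

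*Combined protocol and SAP*

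**What the plan says.** All references are to the combined protocol and SAP.

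- **Specimen.** Study Design / Overview: "We will measure cytokine/chemokine/lipid pain- and inflammation markers in patients' serum". Section 2 (Blood draw: detailed analysis) repeats it: "In serum, the following 39 cytokines/chemokines/lipid mediators/peptides will be measured". The list ends with "VEGF-A, TGF- β , CGRP, Resolvin-D1, Prostaglandin-E2", so all three markers at issue are on it. No plasma sample, clotting time or time to centrifugation is given.
- **Intended meaning.** Section 2 introduces the parameters as "related to pain-associated biomarkers in the systemic circulation" and says of the panel: "These are key mediators and indicators of pain and inflammation".
- **Assays.** Section 2 names a 35-plex kit plus single ELISAs, without saying which marker is run on which.
- **Blood count.** The Overview takes safety tests at baseline and at days 45, 75, 105 and 135, the same draws as the biomarkers: "namely comprehensive metabolic panel and complete blood count with differential, and complete urinalysis". They are planned for safety only.
- **Analysis.** Section 11 (Brief Statistical Analysis Plan) relates markers to pain and activity first "at each time point separately using a linear regression model", and then "by modeling the association across all time points and including time covariate in the linear regression model". Time is the only covariate named.

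**The concern.** Serum is the fluid left after blood has clotted. Clotting activates platelets, which store TGF-β and VEGF-A and release them, and blood cells can form PGE2 in the tube. This is general assay knowledge; the documents neither state nor contradict it. For these three markers the tube therefore adds something to what was circulating at the time of the draw, and the quantity measured differs from the one section 2 says it wants.

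Two things could follow:

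- **Dilution.** If the added part is unrelated to pain, a true association between the circulating marker and pain is weakened. With 20 patients there is little precision to lose.
- **Spurious signal.** If platelet count is related to pain, or if handling differs between visits, the added part can look like an association or a biomarker change. The models do not remove this: the first regression is cross-sectional at each time point, and the second names no patient effect.

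Improvement of serum inflammatory markers is a secondary objective in the Abstract, and the markers are to be related to treatment response. The safety and pain outcomes do not depend on them.

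**Working it through.** **Check of the plan's own figure.** Counting the listed analytes gives 39, as stated. VEGF-A is 35th, TGF-β 36th and PGE2 39th. Since 35 + 4 = 39, list order suggests that VEGF-A is in the 35-plex and that TGF-β, CGRP, resolvin-D1 and PGE2 are the single assays. This is an inference. The plan has no biomarker power calculation to reproduce.

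**Inputs from the documents.** n = 20 completers and p < 0.05 (section 11), taken here as two-sided.

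**Assumptions, none of them in the documents.** The true correlation between circulating marker and pain is 0.60. A share s of the mean serum value is clot-released. The circulating and clot-released parts are independent. Their coefficients of variation (CV) are equal, or stand in ratio k (clot-released to circulating).

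**Dilution.** The circulating part's share of the variance is

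f = (1−s)² / [(1−s)² + (k·s)²],

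and the observed correlation is r = 0.60·√f. Power by Fisher's z is the two-sided normal probability at 0.05 with mean atanh(r)·√(20−3).

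Example, s = 0.30, k = 1: f = 0.49/(0.49+0.09) = 0.845; r = 0.60 × 0.919 = 0.55; atanh(r)·√17 = 0.6205 × 4.123 = 2.56; power = Φ(2.56−1.96) = 73%.

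| Clot-released share s (k = 1) | Observed r | Power, n = 20 |
|---|---|---|
| 0 | 0.60 | 82% |
| 10% | 0.60 | 81% |
| 20% | 0.58 | 78% |
| 30% | 0.55 | 73% |
| 50% | 0.42 | 46% |
| 70% | 0.24 | 17% |
| 90% | 0.07 | 6% |

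The equal-CV assumption matters. With k = 0.5 and s = 0.50, f = 0.25/(0.25+0.0625) = 0.80, r = 0.54 and power is 70% instead of 46%.

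**Spurious signal.** This was simulated with 20,000 data sets per setting, n = 20, and the artefact expressed as a share of marker variance. The circulating part was unrelated to pain, and platelet count correlated 0.3 with pain. The unadjusted false-positive rate was about 15% when the artefact was 50% of the variance and 19% at 75%. With platelet count in the model it was about 5%.

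**What the covariate can recover.** In the same simulations, with a true correlation of 0.60 and platelet count capturing the whole artefact, adjusted power stayed at 81–82%. If platelet count captures only half the clot-released variation, then at s = 0.70, k = 1: f = 0.09/(0.09 + 0.5 × 0.49) = 0.269; r = 0.31; atanh(r)·√(20−1−3) = 0.322 × 4 = 1.29; power is about 25%, against 17% unadjusted. The covariate helps only as far as platelet count explains the artefact.

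**The case against.** The strongest reply is that no size is known. A reader might infer that the serum values of these markers mainly reflect platelets and clotting, or rise in proportion to platelet count and clotting time. The documents do not support either statement: they give no platelet share, no proportionality and no assay property. At clot-released shares up to 30% the power loss in the illustration is under 10 percentage points, and less if the clot-released part varies little between samples. The 0.60 is itself assumed; at a true correlation of 0.30, power at n = 20 is about 25% with no artefact at all. This objection stands and limits the point to an ex vivo part of unstated size.

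Second, the Abstract and Overview name serum markers as the quantity of interest, so a serum level is not simply the wrong endpoint. This stands in part: the mismatch is with section 2, which reads the values as systemic.

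Third, silence on handling does not show that handling varies, and a laboratory manual may fix it. That is fair, but fixed handling would not turn serum into plasma or put a platelet term in section 11.

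Fourth, the remedies have limits. Moving VEGF-A to plasma would probably need a separate assay or a second multiplex run. Platelet count measures neither clotting time nor PGE2 formed in the tube. Both points stand and shape the fix.

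Finally, this is three of 39 markers in work the Overview calls ancillary, so the priority is low.

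**Conclusion.** The point holds in limited form. For TGF-β, VEGF-A and PGE2 the plan measures serum, interprets the result as circulating, and makes no allowance in its regressions for what clotting adds, although a blood count from the same draw is available. Followed as written, this gives a poorer measurement of the stated target than is readily obtainable.

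The size cannot be computed from the documents. Across assumed shares from 0 to 90%, illustrative power runs from 82% to 6%. A reader might take the low end as the expected loss; nothing in the documents favours it over the high end, where the loss is trivial. The figures rest on the assumed 0.60, on independence of the two parts and on their relative CVs.

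This is a minor improvement to exploratory analyses. Specimen type cannot be changed after collection; the covariate and the labelling can still be added at analysis.

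**What to change.** **Section 2 (and the matching sentence in the Overview).** Run TGF-β and PGE2, which by list order appear to be single ELISAs, on EDTA plasma from the same venepuncture, centrifuged within a fixed time to remove platelets. Confirm that the extra tube fits the 45 ml cap, since planned volumes are not stated and the baseline draw also supplies DNA. Keep serum, with a fixed clotting time, for the multiplex, including VEGF-A.

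**Section 11.** For VEGF-A, and for TGF-β if it stays in serum, add a sensitivity regression with the same-draw platelet count as a covariate, and report it beside the unadjusted result. Label serum results for these markers as clot-inclusive. Do not rely on platelet count to correct PGE2 or variation in clotting time.

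**Cost.** One plasma tube per draw, a second sample type to track, and one degree of freedom in the sensitivity model. The blood count is already collected.
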